5.9.2 Samples Handling and Shipment

Pharmacokinetic and pharmacodynamic sample processing, storage, and shipment instructions will be detailed in the laboratory manual.

5.9.3 Analytical Procedures

Plasma samples will be analyzed to determine the concentrations of HMPL-523 CCI using a validated Liquid Chromatography-Tandem Mass Spectrometry method. If required, the plasma samples may be analyzed to document the presence of CCI using a qualified research method.

Chemokines (CCL22, CXCL13, CCL3, etc.) levels in plasma samples will be determined using a multiplex array.

6 ASSESSMENT OF SAFETY

6.1 Safety Plan

Patients will be evaluated clinically and with standard laboratory tests before and at regular intervals during their participation in this study. Safety evaluations will consist of medical interviews, recording of TEAEs, physical examinations, and laboratory measurements.

No evidence available at the time of the release of this protocol indicates that special warnings or precautions are appropriate, other than those will be noted in the HMPL-523 IB.

6.2 Safety Parameters and Definitions

Safety assessments will consist of monitoring and recording AEs and SAEs; measurement of protocol-specified hematologic, clinical chemistry, and urinalysis variables; measurement of protocol-specified vital signs; and other protocol-specified tests that are deemed critical to the safety evaluation of the study drug.

The sponsor or the sponsor's designee is responsible for reporting the relevant SAEs to the applicable regulatory authorities and participating investigators, in accordance with ICH guidelines and local regulatory requirements.

6.2.1 Adverse Event

An AE is any untoward medical occurrence in a clinical investigation subject administered a pharmaceutical product and which does not necessarily have a causal relationship with this treatment. An AE can be any of the following:

- Any unfavorable and unintended sign (including an abnormal laboratory finding), symptom, or disease temporally associated with the use of a medicinal product, whether or not considered related to the medicinal product
- Any new disease or exacerbation of an existing disease (a worsening in the character, frequency, or severity of a known condition), except those described in Section 6.4.8
- Recurrence of an intermittent medical condition (eg, headache) not present at baseline
- Any deterioration in a laboratory value or other clinical test (eg, ECG, X-ray) that is associated with symptoms or leads to a change in study treatment or concomitant treatment or discontinuation from the study drug
- Related to a protocol-mandated intervention, including those that occur prior to assignment of study treatment (eg, screening invasive procedures such as biopsies)

6.2.2 Serious Adverse Events

An SAE is any AE that meets any of the following criteria:

- Fatal (ie, the AE actually causes or leads to death, except for deaths caused by the progress of the disease)
- Life threatening (ie, the AE, in the view of the investigator, places the patient at immediate risk of death; it does not refer to an event that hypothetically might have caused death if it were more severe)
- Requires or prolongs inpatient hospitalization (excluding emergency or outpatient treatment)

- Results in persistent or significant disability/incapacity (ie, the AE results in substantial disruption of the patient's ability to conduct normal life functions)
- A congenital anomaly/birth defect in a neonate/infant born to a female patient or female partner of a male patient exposed to the investigational product(s)
- Considered a significant medical event by the investigator (eg, may jeopardize the patient or may require medical/surgical intervention to prevent one of the outcomes listed above)

All AEs that do not meet any of the criteria for serious should be regarded as nonserious AEs.

The terms "severe" and "serious" are not synonymous. Severity refers to the intensity of an AE (as in mild, moderate, or severe pain); the event itself may be of relatively minor medical significance (such as severe headache). "Serious" is a regulatory definition and is based on patient or event outcome or action criteria usually associated with events that pose a threat to a patient's life or vital functions. Seriousness (not severity) serves as the guide for defining regulatory reporting obligations.

Severity and seriousness should be independently assessed when recording AEs and SAEs on the CRF.

SAEs are required to be reported by the investigator to the sponsor immediately (ie, no more than 24 hours after learning of the event; see Section 6.5.1 for reporting instructions and Section 6.3.1 for AE reporting period).

All SAEs will be followed until resolution, stabilization, the event is otherwise explained, or the participant is lost to follow-up. Depending on the event, follow-up may require additional tests or medical procedures as indicated and/or referral to a general physician or a medical specialist. All pregnancies that occur during participation in the study should be followed to determine the outcome of the pregnancy.

6.2.3 Protocol-Defined Events of Special Interest Expedited Adverse Events

Nonserious AEs of special interest are required to be reported by the investigator to the sponsor immediately (ie, no more than 24 hours after learning of the event; see Section 6.5.1 for reporting instructions). AEs of special interest for this study include the following:

- Hepatotoxicity, including cases of potential drug-induced liver injury (DILI) that include an elevated ALT or AST in combination with either elevated bilirubin or clinical jaundice, as defined by Hy's Law (see Section 6.4.5 and Appendix 13)
- Infective pneumonia
- Interstitial lung disease/Pneumonitis
- Kidney injury

6.2.4 Reporting of Dose-Limiting Toxicity

Investigators will be required to confirm the presence of DLT for each patient enrolled in the dose escalation stage of the study within 2 business days after learning of the event. Investigators will also participate in regular teleconference SRC meetings with the medical monitor and the sponsor, during which they will report any DLTs observed during the DLT assessment window for each patient in the dose-escalation stage of the study. The SRC recommendation form will be completed and signed after the dose escalation meeting by the chairperson of the SRC.

6.3 Methods and Timing for Capturing and Assessing Safety Parameters

The investigator is responsible for ensuring that all AEs and SAEs (as defined in Section 6.2) are recorded on the patient's source documentations and CRF and reported to the sponsor or the sponsor's designee in accordance with protocol instructions.

6.3.1 Adverse Event Reporting Period

After informed consent has been obtained, all SAEs regardless of attribution will be collected until 30 days after the last administration of study treatment or study discontinuation/termination, whichever is later.

After initiation of study medications, all AEs regardless of attribution will be collected until 30 days after the last administration of study treatment or study discontinuation/termination, whichever is later. After this period, the investigators should report only SAEs that are related to prior HMPL-523 treatment (see Section 6.7).

6.3.2 Eliciting Adverse Events

A consistent methodology of nondirective questioning for eliciting AEs at all patient evaluation time points should be adopted. Examples of nondirective questions include:

- “How have you felt since your last clinic visit?”
- “Have you had any new or changed health problems since you were last here?”

6.3.3 Assessment of Severity and Causality of Adverse Events

Investigators will seek information on AEs and SAEs at each patient contact. All AEs and SAEs, whether reported by the patient or noted by authorized study personnel, will be recorded in the patient's medical record and on the appropriate AE/SAE form.

For each AE and SAE recorded on the source documentation and CRF, the investigator will make an assessment of seriousness (see Section 6.2.2 for seriousness criteria), severity, and causality.

Table 4 provides guidance for grading AE severity, and Table 5 provides guidance for assessing the causal relationship to the investigational product.

AE grading should be in accordance with NCI CTCAE v5.0. For AE terms that cannot be found in CTCAE v5.0, general guidelines for AE grading (severity), provided in Table 4, will be used for assessing AE severity.

Investigators should use their knowledge of the patient, the circumstances surrounding the event, and an evaluation of any potential alternative causes to determine whether or not an AE is considered to be related to the study drug. To ensure consistency of causality assessments, investigators should apply the general guidelines provided in Table 5.

Table 4 AEs Grading (Severity) Scale

Grade	Severity	Alternate Description ^a
1	Mild (apply event-specific NCI CTCAE grading criteria)	Asymptomatic or mild symptoms; clinical or diagnostic observations only; intervention not indicated
2	Moderate (apply event-specific NCI CTCAE grading criteria)	Minimal, local, or noninvasive intervention indicated; limiting age-appropriate instrumental ADL ^b
3	Severe (apply event-specific NCI CTCAE grading criteria)	Severe or medically significant but not immediately life threatening; hospitalization or prolongation of hospitalization indicated; disabling; limiting self-care ADL ^c
4	Very severe, life threatening, or disabling (apply event-specific NCI CTCAE grading criteria)	Life-threatening consequences; urgent intervention indicated
5	Death related to AE	

Abbreviations: ADL = activities of daily living; AE = adverse event; CTCAE = Common Terminology Criteria for Adverse Events; NCI = National Cancer Institute; SAE = serious adverse event.

Note: NCI CTCAE v5.0: https://ctep.cancer.gov/protocolDevelopment/electronic_applications/ctc.htm

Note: Regardless of severity, some events may also meet regulatory seriousness criteria. Refer to definition of a SAE (see Section 6.2.2).

- ^a Use these alternative definitions for Grade 1, 2, 3, and 4 events when the observed or reported AE is not in the NCI CTCAE listing.
- ^b Instrumental ADL refers to preparing meals, shopping for groceries or clothes, using the telephone, managing money, etc.
- ^c Self-care ADL refer to bathing, dressing and undressing, feeding self, using the toilet, taking medications, and not bedridden.

Table 5 Causality Attribution Guidance

Causality	Guidance
Related	An AE will be considered “related” to the use of the investigational drug if there is a reasonable possibility that the event may have been caused by the product under investigation. Factors that point toward this assessment include, but are not limited to, a positive rechallenge, a reasonable temporal sequence between administration of the drug and the event, a known response pattern of the suspected drug, improvement following discontinuation or dose reduction, a biologically plausible relationship between the drug and the AE, or a lack of an alternative explanation for the AE.
Not Related	An AE event will be considered “not related” to the use of the investigational drug if there is not a reasonable possibility that the event has been caused by the product under investigation. Factors pointing toward this assessment include, but are not limited to, the lack of reasonable temporal relationship between administration of the drug and the event, the presence of a biologically implausible relationship between the product and the AE, or the presence of a more likely alternative explanation for the AE.

AE = adverse event.

The above guidance should be taken into consideration when deciding if there is a “reasonable possibility” that an AE may have been caused by the drug.

If the investigator decides that the SAE is not related to the study drug, the investigator must provide another cause of event for the SAE. If the investigator decides that the SAE is related to the study drug, the investigator should provide the rationale of causality to the study medication.

6.4 Procedures for Recording Adverse Events

Investigators should use correct medical terminology/concepts when recording AEs or SAEs on the CRF. They should avoid colloquialisms and abbreviations.

All AEs (including SAEs) should be recorded on the AE CRF, and the check box for “Serious” should be ticked for entries that fit the criteria of serious. The investigator should also complete an SAE reporting form and submit this to the sponsor or the sponsor’s designee within 24 hours of knowledge of the event.

Only 1 AE term should be recorded in each event field on the CRF.

6.4.1 Diagnosis Versus Signs and Symptoms

If known, a diagnosis should be recorded on the CRF rather than individual signs and symptoms (eg, record only liver failure or hepatitis rather than jaundice, asterixis, and elevated transaminases). However, if a constellation of signs and/or symptoms cannot be medically characterized as a single diagnosis or syndrome at the time of reporting, each individual event should be recorded as an AE or SAE on the CRF. If a diagnosis is subsequently established, it should be reported as follow-up information.

6.4.2 Adverse Events Occurring Secondary to Other Events

In general, AEs occurring secondary to other events (eg, cascade events or clinical sequelae) should be identified by their primary cause with the exception of severe or serious secondary events. For example, if severe diarrhea is known to have resulted in mild dehydration, it is sufficient to record only diarrhea as an AE or SAE on the CRF.

However, medically significant AEs occurring secondary to an initiating event that are separated in time should be recorded as independent events on the CRF. For example, if a severe gastrointestinal hemorrhage leads to renal failure, both events should be recorded separately on the CRF.

6.4.3 Persistent or Recurrent Adverse Events

A persistent AE extends continuously, without resolution, between patient evaluation time points. Such events should only be recorded once in the CRF unless their severity increases. If a persistent AE becomes more severe, it should be recorded again on an AE/SAE CRF.

A recurrent AE occurs and resolves between patient evaluation time points and subsequently recurs. All recurrent AEs should be recorded on an AE/SAE CRF, respectively.

6.4.4 Abnormal Laboratory Values

Only clinically significant laboratory abnormalities that require active management will be recorded as AEs or SAEs on the CRF (eg, abnormalities that require study drug dose modification, discontinuation of study treatment, more frequent follow-up assessments, further diagnostic investigation, etc).

If the clinically significant laboratory abnormality is a sign of a disease or syndrome (eg, ALP and bilirubin 5× ULN associated with cholecystitis), only the diagnosis (eg, cholecystitis) needs to be recorded on the AE/SAE CRF.

If the clinically significant laboratory abnormality is not a sign of a disease or syndrome, the abnormality itself should be recorded as an AE or SAE on the CRF. If the laboratory abnormality can be characterized by a precise clinical term, the clinical term should be recorded as the AE or SAE. For example, an elevated serum potassium level of 7.0 mmol/L should be recorded as “hyperkalemia”.

Observations of the same clinically significant laboratory abnormality from visit to visit should not be repeatedly recorded as AEs or SAEs on the CRF, unless their severity, seriousness, or etiology changes.

6.4.5 Abnormal Liver Function Test Results

The finding of an elevated ALT or AST in combination with either an elevated total bilirubin ($> 2 \times \text{ULN}$) or clinical jaundice in the absence of cholestasis or other causes of hyperbilirubinemia is considered to be an indicator of severe liver injury (as defined by Hy’s Law). Therefore, investigators must report an AE of special interest upon the occurrence of either of the following:

- Treatment-emergent ALT or AST $\geq 3 \times \text{ULN}$ in combination with total bilirubin $> 2 \times \text{ULN}$
- Treatment-emergent ALT or AST $\geq 3 \times \text{ULN}$ in combination with clinical jaundice

The most appropriate diagnosis or (if a diagnosis cannot be established) the abnormal laboratory values should be recorded on the AE CRF (see Section 6.4.1) and reported to the sponsor’s designee as a nonserious AE of special interest (see Section 6.5.1).

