6.5 Expedited Reporting From Investigator to Sponsor

Certain events require immediate reporting to allow the sponsor to take appropriate measures to address potential new risks in a clinical trial. The investigator must report such events on specific reporting forms to the sponsor (see form completion guideline for contact detail) immediately; under no circumstances should reporting take place more than 24 hours after the investigator learns of the event. The following is a list of events that the investigator must report to the sponsor within 24 hours after learning of the event, regardless of relationship to the study drug:

- SAEs (see Section 6.5.1 for further details)
- Nonserious AEs of special interest (see Section 6.5.1 for further details)
- Pregnancies

6.5.1 Reporting Requirements for All Serious Adverse Events and Protocol-Defined Events of Special Interest

Investigators will submit reports of all SAEs and protocol-defined events of special interest, regardless of attribution, to the sponsor or the sponsor's designee via fax or email within 24 hours of learning of the events.

For initial SAEs and protocol-defined events of special interest reports, investigators should record all case details that can be gathered within 24 hours on a SAE reporting form. Relevant follow-up information should be submitted to the sponsor or the sponsor's designee as soon as it becomes available and/or upon request within 24 hours of the investigator's awareness of the events.

Investigators must also comply with local requirements for reporting SAEs to the local health authority and IRB/IEC.

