6.5.2 Regulatory Reporting Requirements for Serious Adverse Events

Prompt notification of SAEs by the investigator to the sponsor is essential so that legal obligations and ethical responsibilities towards the safety of patients are met.

The sponsor has a legal responsibility to notify both the local regulatory authority and other regulatory agencies about the safety of a product under clinical investigation. The sponsor will comply with country-specific regulatory requirements relating to safety reporting to the regulatory authority, IRB/IEC, and investigators.

Investigator safety reports are prepared for suspected unexpected serious adverse reactions according to local regulatory requirements and sponsor policy and are forwarded to investigators as necessary.

An investigator who receives an investigator safety report describing a SAE(s) or other specific safety information (eg, summary or listing of SAEs) from the sponsor will file it with the IB and will notify the IRB/IEC, if appropriate according to local requirements.

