APPENDIX 13 CLINICAL EVALUATION OF POSSIBLE DRUG-INDUCED LIVER INJURY

If alanine aminotransferase (ALT) or aspartate aminotransferase (AST) is elevated to higher than $3 \times$ upper limit of normal (ULN) **and** bilirubin is elevated to higher than $2 \times$ ULN, HMPL-523 treatment should be discontinued immediately, and supportive treatment should be given. This combination of laboratory abnormalities meets the biochemical criteria for Hy's Law, which is associated with a markedly increased possibility of severe drug-induced liver injury (DILI) and may progress to liver transplantation or death (FDA 2009).

If the biochemical criteria for Hy's Law are met, HMPL-523 should be immediately discontinued, and patients need to be very closely monitored (bilirubin, alkaline phosphatase (ALP), AST, and ALT measured 2-3 times weekly until the results return to baseline or normal) and other causes of liver injury evaluated (eg, new or worsening hepatobiliary metastases; nonmalignant biliary obstruction; viral hepatitis A, B, or C; alcoholic or autoimmune hepatitis; preexisting or acute liver disease; ischemic liver injury; right-sided congestive heart failure; new or worsening liver metastases; or concomitant medication that could cause the observed injury). Consultation with a gastroenterologist or hepatologist should be considered.

If the biochemical criteria for Hy's Law have been met, expedited reporting is required (see Section 6.5.2), before waiting for the evaluation of other causes to be completed.

Recommended Data Collection for Suspected DILI

The investigator is recommended to obtain the following information so as to further evaluate, follow up and complete the clinical data. Data should be recorded on case report forms (CRFs), where possible, and supplemented by investigator reporting as text in the clinical database:

- Medical history of the patient:
 - Detailed history of current symptoms, diagnosis of complications, and medical history
 - Previous medical history (viral hepatitis, alcoholic hepatitis, autoimmune disease, biliary tract disease, cardiovascular disease, etc)
 - History of concomitant medication (including over-the-counter and prescription drugs, herbal medicines, and dietary supplements), alcohol consumption, recreational drugs, and special diet
 - History of exposure to potentially hepatotoxic chemicals
- Complete the following laboratory tests:
 - Hematology

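### Protocol 6.4.5 sends every Hy's Law-pattern case to the sponsor as a nonserious event, with no exception for a case that meets a seriousness criterion

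*Protocol*

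**What the plan says.** Section 6.4.5 describes raised transaminases with raised bilirubin or jaundice, without cholestasis or another explanation, as a marker of severe liver injury. Investigators must report an AE of special interest when treatment-emergent ALT or AST is at least 3 times ULN together with total bilirubin above 2 times ULN or clinical jaundice. The diagnosis, or failing that the laboratory abnormality, goes on the AE CRF, and the case is reported to the sponsor's "designee as a nonserious AE of special interest (see Section 6.5.1". No exception follows.

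The general rules are elsewhere:

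- Section 6.3.3, for each recorded AE: "the investigator will make an assessment of seriousness (see Section 6.2.2 for seriousness criteria), severity, and causality".
- Section 6.2.2 lists the seriousness criteria, including "Considered a significant medical event by the investigator (eg, may jeopardize the patient", and asks that severity and seriousness be judged separately on the CRF.
- Section 6.4 says the Serious box "should be ticked for entries that fit the criteria of serious".

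Appendix 13 says of ALT or AST above 3 times ULN with bilirubin above 2 times ULN that "expedited reporting is required (see Section 6.5.2), before waiting for the evaluation of other causes to be completed". Section 6.5.2 is the SAE section and opens with "Prompt notification of SAEs by the investigator to the sponsor is essential". Section 6.5.1, which 6.4.5 cites, covers SAEs and protocol-defined events of special interest together.

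SAP 17.2.7 and 17.2.8 take seriousness from the Adverse Events page of the eCRF. A missing entry is counted as serious; an entered value stands.

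**The concern.** Sections 6.2.3 and 6.5 use nonserious AEs of special interest as the name of a reporting class, and 6.5 lists that class separately from SAEs. Section 6.4.5 puts every Hy's Law-pattern case in it. For a case that meets a 6.2.2 criterion, the event-specific instruction therefore gives a different answer from the general one.

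Hepatotoxicity is named as an important identified risk in Section 2.3.2.1. A site that treats the event-specific text as controlling could enter a qualifying case as nonserious on the eCRF. The case would then be missing from the serious TEAE table, the drug-related serious TEAE table and the serious lines of the AE overview. Those are the outputs in which a reader would look for serious liver harm.

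**Working it through.** The documents give no figure to reproduce on this point, and no rate of Hy's Law cases in this study can be read from them. The check is a comparison of texts, followed by a trace into the outputs.

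**1. Is there an exception anywhere?** Section 6.4.5 has none. Sections 6.2.3 and 6.5 speak of nonserious AEs of special interest and do not say how a serious one is to be labelled. Section 6.5.1 handles both classes but does not amend 6.4.5.

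**2. Can a case covered by 6.4.5 be serious?** Yes. Section 6.4.5 points to 6.4.1 for the diagnosis, and 6.4.1 uses liver failure or hepatitis as its example of what to record in place of jaundice and raised transaminases. A patient with liver failure may well be hospitalized or in danger, and either can meet 6.2.2. Appendix 13 says the pattern "may progress to liver transplantation or death", which is close in sense to the medical-significance criterion, although that criterion is left to the investigator.

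**3. Which rule governs the Serious box?** Sections 6.2.2, 6.3.3 and 6.4 do. The word in 6.4.5 is attached to the report sent to the sponsor's designee, not to the CRF field. A site following all the text should tick the box and still meets an instruction to report the event as nonserious.

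**4. What follows if the box is wrong?**

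| Output | Qualifying case entered as nonserious |
|---|---|
| Serious and drug-related serious TEAE tables (SAP 17.2.7, 17.2.8) | Not counted |
| AE and AESI listings (SAP 17.2) | Shown |
| AESI table (SAP 17.2.9) | Shown if treatment-emergent and the preferred term falls in the hepatic queries |
| Combined liver-test rows (SAP 17.4) | Shown if bilirubin reaches 2 times ULN; a case that qualifies only on jaundice appears in the transaminase rows |
| Discontinuation table (SAP 17.2.6) | Expected for an on-drug case, since Appendix 15 Table 8 requires permanent discontinuation |
| DLT summary and listing (SAP 17.1) | Expected in Stage 1 Cycle 1 for an evaluable patient, since Section 4.4 makes any Hy's Law case a DLT unless clearly unrelated |

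**5. Late cases.** SAP 17.2 ends the TEAE period 30 days after the last dose, or at new anti-neoplastic therapy if earlier, and afterwards admits only related SAEs. A related case arising later and marked nonserious is therefore not a TEAE. It also drops out of the AESI table, whose categories in SAP Table 3 are defined on TEAEs. The listings and laboratory rows still show it. No fixed end date applies: Section 6.3.1 collects AEs to 30 days after the last dose or to study discontinuation, whichever is later, and the SAP's late-SAE rule has no upper limit.

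**The case against.** The strongest reply is that 6.4.5 sets a minimum. On that reading it says: report within 24 hours even when the case is not serious. Its operative sentence requires only an AE of special interest, and three other sections tell the site how to fill in the Serious box. Appendix 13, by pointing to the SAE section, pushes towards serious handling. Reporting speed is not at risk either: for initial SAE and "events of special interest reports, investigators should record all case details that can be gathered within 24 hours on a SAE reporting form", so the form and the 24-hour clock are the same for both classes. Source data verification and queries give a further chance to catch a wrong entry.

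Most of this stands. It limits the point to a conflict between a specific and a general instruction, since a general rule does exist. It does not remove the conflict, because 6.4.5 states the class without condition.

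Four stronger readings are tempting, and the documents do not support them:

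- *Every Hy's Law case is an SAE.* No section says so. Section 6.2.2 separates severe from serious, and its life-threatening criterion excludes events that are only hypothetically fatal.
- *The SAP is at fault.* Taking seriousness from the eCRF field is ordinary practice, and the SAP already treats missing entries conservatively.
- *The bias in the serious TEAE rate can be stated in percentage points.* That would mean dividing an invented number of cases by a cohort size; no count is given.
- *Late cases are exposed only between day 30 and day 37 after the last dose.* The follow-up visit is allowed up to day 37, but AE collection and the late-SAE rule are not bounded there.

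**Conclusion.** Wrong as written, and minor: between an optional clarification and something the sponsor should do. Section 6.4.5 directs all Hy's Law-pattern cases to a nonserious class without excepting those that meet 6.2.2. That contradicts 6.2.2, 6.3.3 and 6.4, and fits poorly with Appendix 13.

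Any effect on the serious TEAE tables depends on two things: that a qualifying case occurs, and that a site carries the wording of 6.4.5 into the Serious field. The number of such cases is unknown and may be zero, so no size can be put on the effect. Such a case would normally remain visible in the AESI, laboratory, discontinuation or DLT outputs, and the sponsor would hear of it just as quickly. The one situation with a wider loss is a related case arising more than 30 days after the last dose, where the flag also decides whether the event is a TEAE.

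**What to change.** 1. In Section 6.4.5, put the words *as an SAE if any criterion in Section 6.2.2 is met, otherwise* in front of the existing nonserious category. A site clarification is enough, or the change can wait for the next amendment: enrollment is closed and about 3 patients remain on treatment.
2. Have Appendix 13 cite Section 6.5.1 for reporting by the site, and Section 6.5.2 in addition when the event is serious.
3. Before database lock, list every patient with ALT or AST at least 3 times ULN plus total bilirubin above 2 times ULN, or plus jaundice, at any time after first dose, whose corresponding AE is marked nonserious. Query the site to confirm seriousness against 6.2.2. This is data cleaning and needs no change to the SAP's definitions.

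The fix should not require every such case to be recorded as serious; that judgement stays with the investigator.

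The cost is one phrase, one cross-reference, one listing and probably a few queries. The reporting form and the 24-hour clock do not change. The SAE count may rise slightly if a case is reclassified.
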